9.2 Protocol Deviations

The following listings will be provided for the Enrolled Analysis Set:

- All inclusion / exclusion and major protocol deviations.
- All other protocol deviations.

9.3 Demographic and Baseline Characteristics

9.3.1 Demographics

The following demographic characteristics will be summarized using descriptive statistics or frequency counts, as appropriate:

- Age,
- Age group (< 65 years and \geq 65 years),
- Sex,
- Ethnicity,
- Race and racial combinations,
- Height,
- Weight,
- BMI,
- Diagnosis of HIV,
- Diagnosis of HBV,
- Diagnosis of HCV.

The weight to be summarized as part of demographics will be the dry weight based on medical history. If the dry weight is missing, the weight at Screening will be used. If the weight at Screening is missing, the Day 1 weight will be used. Demographics will be summarized for the RWS Analysis Set and overall and for RiS Analysis Set.

9.3.2 Baseline Characteristics

The following will be summarized using descriptive statistics or frequency counts, as appropriate:

- Allograft / allograft donor characteristics,
- Diagnosis and disease characteristics.

Baseline characteristics will be summarized for the RWS Analysis Set and overall and for RiS Analysis Set.

- Allograft / allograft donor characteristics: age, sex, ethnicity, race, biological relative, blood group, status at time of donation (alive, dead), deceased donor donation type (donation after brain death, donation after circulatory death), deceased donor criteria (kidney standard criteria donor, kidney expanded criteria donor), Kidney Donor Profile

Index (KDPI score), Human Immunodeficiency Virus (HIV) (yes, no), Hepatitis B Virus (HBV) (yes, no), Hepatitis C Virus (HCV) (yes, no),

- Diagnosis and disease characteristics: time since most recent renal transplant, time since AMR diagnosis, time since most recent rejection episode, severity of current AMR episode, total number of renal transplants, primary reason for kidney transplant (diabetes [type 1 and 2], hypertension, polycystic kidney disease, drug toxicity [non-steroidal anti-inflammatory drugs or others], IgA nephropathy, rapidly progressive neuropathy, membranous glomerulopathy, other nephritides, renal artery stenosis, other infectious diseases [HIV; hepatitis; endotoxin], congenital nephropathy [primary NOS], stone disease, renal cancer, other), delayed graft function (yes, no), dialysis within 14 days after most recent transplant (yes, no), presence of DSA prior to kidney transplant (yes, no), de novo DSA post-transplant (yes, no).

The following listings will be provided for RWS Analysis Set and overall and for RiS Analysis Set:

- Demographic characteristics,
- Allograft / allograft donor characteristics,
- Diagnosis and disease characteristics.

9.4 Prior and Concomitant Medications

Prior and Concomitant medications will be coded using CSL Behring Drug coding dictionary (WHO-DDE Enhanced 2016MAR, B2 Format), summarized, and listed. The summary of prior and concomitant medications will show the number and percentage of subjects taking prior/concomitant medications. Anatomical Therapeutic Chemical (ATC) classification Level 1 (Body System) information will be included in the dataset created but will not appear on the listing or summary. ATC Level 4 and preferred term of prior/concomitant medications will be used for summaries and listings. If the ATC Level 4 coding is not available for a preferred term, the next available lower level ATC code will be used. The summary will be provided by treatment group for RWS Analysis Set and overall for the RiS Analysis Set.

Concomitant medication start and end dates relative to treatment start and end dates are used to select data to include in summaries as follows:

- Summary of Concomitant Medications: This summary will contain medications with start dates relative to treatment assigned to ('BEFORE', 'DURING') and end dates relative to treatment assigned to ('DURING', 'AFTER').

- Summary of Concomitant Medications with On-Therapy Onset: This summary will contain medications with start dates relative to treatment assigned ('DURING') and end dates relative to treatment assigned to ('DURING', 'AFTER').

In the summary of concomitant medications, each subject is counted once within each unique term. For example, if a subject takes Amoxycillin on two separate occasions, the subject is counted only once under the ingredient "Amoxycillin".

Concomitant medications will be summarized separately for medications with onset date within the on-therapy period and for medications with onset date within the before-therapy period.

Note: In order to be considered a concomitant medication, the concomitant medication must have been taken at some point during the on-therapy window.

Concomitant medications will be summarized for the RWS Analysis Set and overall and for RiS Analysis Set.

9.5 Medical History

Medical history by body system will be summarized in a frequency table by treatment group for RWS Analysis Set and overall and for RiS Analysis Set.

Medical history will also be presented in a by-subject listing for RiS Analysis Set.

10 Efficacy

All efficacy summary will be based on mITT Analysis Set of subjects for Period 2 unless otherwise specified. All efficacy summary will be based on RiS Analysis Set for Period 1 unless otherwise specified.

Subject listings will be provided for the efficacy information based on the mITT Analysis Set.

10.1 Analysis of Proportion of Subjects With Loss of Response at the End-of-TP2

The number and proportion of subjects with loss of response at the End-of-TP2 will be presented by treatment group along with the confidence interval for the difference between the two groups.

Subjects will be considered to have lost response if they drop-out or are lost to follow-up before the response status at the End-of-TP2 could be determined.

Components of loss-of-response at the End-of-TP2 will be summarized by treatment groups in terms of the proportion of subjects with:

- End-of-TP2 eGFR (mean of Week 36 and Week 38 eGFR values) that is not stable, defined as:
 - End-of-TP2 eGFR that is < 90% of the End-of-TP1 eGFR for subjects whose End-of-TP1 eGFR is \geq 100% of baseline,
 - End-of-TP2 eGFR that is < 90% of baseline for subjects whose End-of-TP1 eGFR is \geq 90% of baseline and < 100% of baseline,
- All-cause allograft failure (ie, allograft nephrectomy, or institution of permanent dialysis, or return to the transplant waitlist for renal transplant),
- Death by any cause.

The primary efficacy analysis will be conducted for the mITT Analysis Set.

10.1.1 Subgroup Analyses of Proportion of Subjects With Loss of Response at the End-of-TP2

The proportion of subjects with loss of response at the End-of-TP2 will be summarized by the treatment group for the following subgroups based on the following subgroup analyses outlined below will be conducted for the mITT Analysis Set.

The following subgroups, and possibly others to be described in the SAP, will be summarized by treatment group with respect to the proportion of loss-of-response:

- Geographic region: USA, non-USA,
- DSA by randomization strata: sensitized, de novo,
- DSA by classification: HLA class I, HLA class II, both HLA class I and II,
- AMR severity: severe, non-severe (all other severities),
- Type of donor: deceased, living,
- Recipient race: Black, non-Black,
- Recipient sex: Male, Female,
- Recipient age: < 65 years, \geq 65 years.

The difference in the proportion of response along with the 95% confidence interval will be also presented for each subgroup.

10.2 Analysis of key Secondary Endpoint Proportion of Subjects With All-Cause Allograft Failure Through the Responder Follow-up Period (ie, Within 48 Months After Enrollment)

No subject will complete the follow-up period of 48 months after enrollment. Therefore, this key secondary analyses cannot be conducted.

10.3 Analysis of Time to All-Cause Allograft Failure Through 48 Months After Enrollment

No formal analysis will be conducted for time to all-cause allograft failure since no subject will complete 48 months after enrollment.

A by-listing of all-cause allograft failure information will be provided for the mITT Analysis Set.

10.4 Analysis of the Change in eGFR From Baseline to End-of-TP1

This analysis will be based on the RiS Analysis Set.

The eGFRs during Treatment Period 1 (ie with open-label C1-INH) will be summarized by scheduled visit using descriptive statistics for the observed values, and changes from baseline (ie missing data will be not imputed).

10.5 Analysis of Responders at the End-of-TP1

This analysis will be based on the RiS Analysis Set.

The proportion of responders at the End-of-TP1 will be presented together with an exact 95% confidence interval. Definition of response at End-of-TP1 is given in [Section 8.2.9](#).

10.6 Analysis of the Change in eGFR From End-of-TP1 to the End-of-TP2

No formal analysis for the change in eGFR from End-of-TP1 to the End-of-TP2 will be conducted.

A by-listing for eGFR of all individual values will be provided. for the mITT Analysis Set.

10.7 Analysis of the Rate of Change of eGFR in Treatment Period 2

No formal analysis of the rate of change of eGFR in Treatment Period 2 will be conducted due to the small number of subjects completing TP2. Mean plot for the change in eGFR from baseline in Treatment Period 2 will be provided for the subjects in the mITT Analysis Set.

10.10 Analysis of C1-INH Functional Activity

PK parameter of C_{max} and AUC_{0-t} for C1-INH functional activity will be presented in a by-subject listing for the PK Analysis Set (see [Section 12](#)).

10.12 Analysis of Plasmapheresis Sessions

The total number plasmapheresis sessions will be derived for each subject and provided in a by-listing for the mITT Analysis Set.

10.13 CCI

CCI

[figure not shown]
10.14 CCI

CCI

10.15 CCI

CCI

10.16 CCI

CCI

10.17 CCI

CCI

10.18 Trough IVIg Concentrations at Designated Time Points

A by-listing of trough IVIg concentrations at will be presented for the RiS Analysis Set at Week 12 and for the mITT Analysis Set at Week 32.

10.19 CCI

CCI

10.20 Treatment Compliance

Percentage compliance will be a function of the amount of IMP taken, ie, the actual cumulative administered volume (mL), and the amount of IMP prescribed, ie, the cumulative planned volume (mL).

Percentage compliance to IMP will be calculated as:

compliance (%) = (cumulative administered volume / cumulative planned volume)*100.

Percentage compliance will be summarized by frequencies of < 80%, 80% – 120%, > 120%.

Percentage compliance will be summarized for the RiS Analysis Set for Treatment Period 1 and by treatment group for the mITT Analysis Set for Treatment Period 2. Percentage compliance will be also summarized for the entire study for the mITT subjects randomized to C1-INH in period 2. Also, compliance will be summarized based on intravenous delivery and subcutaneous delivery of C1-INH during Treatment Period 1.

Subjects may undergo retreatment during the post-treatment Follow-up Period with the blinded investigational product to which they were randomized in Treatment Period 2.

The following listings will be provided:

- Randomized and actual treatments,
- Drug accountability data (dispensed and returned),
- Overall compliance.

A by-subject listing will be provided including compliance by treatment period, by delivery system (intravenous and subcutaneous), randomized and actual treatments.

Calculation of compliance and extend of exposure (see [Section 11.1](#)) will be based on drug accountability data collected by IRT system (or RAVE) as the eCRF does not contain any such related data fields. Drug accountability data will be part of final study data base.

11 Safety Analyses

Open-label safety events and findings will be defined as those with an onset date prior to the randomization date. Double-blind safety events and findings will be defined as those with an onset date on or after the randomization date.

The RiS Analysis Set will be used for analysis of safety for open label TP1. The RWS Analysis Set will be used for analysis of safety during the double-blind period; summaries will be presented by treatment group and total number of subjects in RWS Analysis Set. Also, safety of RWS subjects randomized to C1-INH will be summarized over the study including periods 1 and 2 and follow-up.

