This is the statistical analysis plan (SAP) for the Clinical Study Report for study CSL842_3001. This SAP provides details of the planned statistical analyses of the primary and relevant secondary endpoints for which data are available. This study was terminated by the sponsor on September 15, 2020 for administrative reasons. At the time of termination, 13 subjects were randomized and 2 subjects were still in treatment (1 subject in TP2 and another subject in re-treatment). The study database will be locked after the completion of the dosing regimens of these 2 subjects. Based on the termination of the study, many analysis discussed in the protocol will not be able to be performed (for example, all 4 year endpoints are unattainable).

[figure not shown]
This SAP complies with the International Conference on Harmonisation (ICH) Harmonised Tripartite Guideline Topic E9, Statistical Principles for Clinical Trials. It is based upon the Clinical Study Protocol (dated 01-March-2017) and Study Protocol Amendment Version 1.0 (dated 30-August-2017), Study Protocol Amendment Version 2.0 (dated 23-January 2019), and Study Protocol Amendment Version 3.0 (dated 31-January 2020).

4 Study Design

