8.3.2 Study Time Periods for AEs

AEs occurring On-Therapy or during Follow-up will be handled as treatment-emergent AEs.

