11.1 Extent of Exposure

The extent of exposure to C1-INH in open-label and in double-blind period and to placebo in double-blind period will be summarized using descriptive statistics. Extent of exposure will be described in terms of the following (including intravenous administration and subcutaneous administrations):

- Cumulative administered volume (mL), calculated as sum of single administered volumes in treatment periods,
- Cumulative planned volume (mL), calculated as sum of single planned volumes in treatment periods (planned administration at days 1, 4, 7, 10, and 13 and twice weekly dosing beginning at the day 14 visit in Treatment Period 1 and twice weekly dosing in Treatment Period 2; dosing scheme must be taken into account for cumulative planned dose depending on subjects time in study; the number of administrations in period of twice weekly dosing will be calculated as: $((\text{date of end of twice weekly dosing} - \text{date of start of twice weekly dosing} + 1) / 7) * 2$,
- Days on treatment, calculated as days between first and last dose in treatment periods;
- Average daily dose, calculated as cumulative administered dose divided by days on treatment for each treatment period,
- For subjects continuing C1-INH in Treatment Period 2 cumulative administered dose, cumulative planned dose, days on treatment and average daily dose will be summarized for the whole C1-INH treatment period.

Extent of exposure for Retreatment Periods will be summarized separately.

For summaries of Treatment Period 1 the RiS Analysis Set will be used. Summaries for Treatment Period 2 will be based on the RWS Analysis Set. Also, exposure summary will be presented for the RWS subjects receiving C1-INH during the entire study (Treatment Period 1 and Treatment Period 2 combined).

A by-subject listing will be provided including treatment period (including re-treatment), cumulative administered volume, cumulative planned volume, days on treatment and average daily dose.

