11.2 Adverse Events

Adverse events will be coded to the Preferred Term (PT) level using the Medical Dictionary for Regulatory Affairs (MedDRA dictionary), version 23.0 or higher. Treatment-emergent AEs (TEAEs) are defined as AEs reported at or after the start of the first infusion. All AEs regardless of when they were reported will be listed.

Summaries of TEAEs will count the number of subjects, not the number of events, that is, subjects with multiple occurrences of the same TEAE will be counted once.

The number and percentage of subjects with TEAEs will be reported. Also, the number and percentage of subjects with serious TEAEs, TEAEs by severity, and serious TEAEs related to investigational product will be presented. Adverse events will be presented for Treatment Period 1 and RiS Analysis Set. For Treatment Period 2 summaries will be presented for the RWS Analysis Set. In addition, the summaries will be given for C1-INH over the whole study for RWS Analysis Set and a summary across the whole study will be given for the RiS Analysis Set.

A summary of number and percentage of subjects with any TEAE by maximum severity or grade will be produced. TEAEs will be sorted by System Organ Class (SOC) and PT in descending order of incidence overall treatment arms. The summary will report the number of subjects with at least one TEAE, counted for the maximum severity and, for each PT reported, the number of subjects for each, counted for the maximum severity.

In addition, the frequency and percentage of TEAEs will be summarized and displayed in two ways: 1) in descending order of incidence in whole study for RiS Analysis Set by PT only and 2) in descending order of incidence whole study for RiS Analysis Set by SOC and PT. In the SOC row, the number of subjects with multiple events under the same system organ class will be counted once.

A separate summary will be provided for study treatment-related serious TEAEs. Missing relationship to study treatment will be imputed as described in [Section 8.1.2](#); this summary will also include the number and percentage of TEAEs with a missing relationship to aid in interpretation of the results.

By-subject listings will also be provided with detailed information to support the different AE summaries.

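### SAP Section 11 gives the double-blind adverse-event period a start but no end, so the by-arm Treatment Period 2 tables can absorb retreatment and follow-up events

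*SAP*

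**What the plan says.** The opening text of SAP Section 11 sets the period split: "Open-label safety events and findings will be defined as those with an onset date prior to the randomization date", and "Double-blind safety events and findings will be defined as those with an onset date on or after the randomization date". The double-blind period is then summarized by arm in the Randomized Withdrawal Safety (RWS) set. SAP 11.2 follows with "For Treatment Period 2 summaries will be presented for the RWS Analysis Set", and SAP 11.3 and 11.4 do the same for events of special interest and serious events. None of these sections gives TP2 a window of its own for adverse events.

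The definitions of treatment emergence do not agree:

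- SAP 11.2: "Treatment-emergent AEs (TEAEs) are defined as AEs reported at or after the start of the first infusion", with no upper limit.
- SAP 8.3.2: "AEs occurring On-Therapy or during Follow-up will be handled as treatment-emergent AEs". SAP 8.3.1 counts retreatment, plus 30 days, as on-therapy.
- SAP 8.2.3: treatment emergence ends 30 days after the investigational product stop date, and later events are post-treatment.

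For exposure, SAP 11.1 does separate retreatment: "Extent of exposure for Retreatment Periods will be summarized separately". No adverse-event section has an equivalent.

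The protocol plans adverse events by TP1 and TP2 (10.3.4.1). It closes the TP1/TP2 observation period 30 days after the last dose in those periods and gives retreatment its own observation period (9.4).

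SAP 11.2 also plans treatment-emergent event displays "in descending order of incidence in whole study for RiS Analysis Set by PT only", and a second display by system organ class and preferred term. The Run-in Safety (RiS) set is everyone dosed with C1-INH in TP1, including those later randomized to placebo.

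**The concern.** The by-arm RWS tables are the only randomized safety comparison left in the trial. Their title says TP2, but the rule that fills them runs on past Week 38. A subject who is retreated has a second stretch of full adverse-event collection, and a subject who is not retreated has none. In follow-up outside retreatment, the protocol requires reporting only of events with at least a possible causal link. The extra events are therefore collected unevenly between subjects and are selected by attributed causality. A secondary endpoint, related adverse events during TP1 and during TP2, is defined by period and is sensitive to this.

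The RiS whole-study tables raise a separate issue. They have one column, so an event during placebo treatment in TP2 or retreatment sits beside events on C1-INH with nothing to tell them apart.

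**Working it through.** The plan states no figure for this point, so there is none to reproduce. The check compares windows and then readings.

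**Inputs**

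- TP2 lasts 25 weeks (protocol 3.4).
- The TP1/TP2 observation period ends 30 days after the last dose (protocol 9.4).
- Retreatment lasts 25 weeks in protocol 8.5.6 and in the notes to protocol Table 5, but 26 weeks in protocol 3.2 and SAP 4.3. These need reconciling; both are carried here.
- Randomized treatment starts at Week 13, and follow-up is planned to Week 208 (protocol Table 3).
- Thirteen subjects were randomized, and one subject was in retreatment at termination (SAP Section 3). The split by arm is not given; 6/7 is assumed.

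**Windows**

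1. TP2 closed at last dose plus 30 days: 25 × 7 + 30 = 205 days.
2. One full retreatment: 25 × 7 + 30 = 205 days, or 26 × 7 + 30 = 212 days.
3. Full collection for a subject with one full retreatment: 205 + 205 = 410 days, or 205 + 212 = 417 days. Ratio to the closed window: 410/205 = 2.00, or 417/205 = 2.03. This assumes that retreatment starts after the 30-day tail has ended.
4. Design ceiling of the SAP 11 rule: (208 − 13) × 7 = 1365 days, and 1365/205 = 6.7. This is a calendar span, not time under full collection, and SAP 8.2.9 states that no subject reached 48 months.

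**Effect of one subject**

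The planned statistic is the percentage of subjects in the arm with an event. One subject whose only event of a given type falls in retreatment adds 1/7 = 14.3 or 1/6 = 16.7 percentage points.

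**What each reading puts in the TP2 tables**

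- SAP 11 with 8.3.2 and 11.2, taken literally: retreatment events in, reported follow-up events in.
- SAP 8.2.3, stop date taken as last retreatment dose: retreatment events in, along with events in the gap before retreatment; events more than 30 days after that dose out.
- SAP 8.2.3, stop date taken as last TP2 dose: everything more than 30 days after that dose out.
- Table label alone, Weeks 13 to 38: retreatment and follow-up events out. Retreatment events in placebo subjects then appear in no by-arm summary, only in the pooled RiS tables and the listings.

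The SAP does not say which definition prevails, so two programmers could produce different tables from it.

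**The case against.** The best defence is the label. SAP 11.2 to 11.4 call these TP2 tables, TP2 is bounded at Weeks 13 to 38 elsewhere, the protocol gives a 30-day tail, and SAP 11 itself names follow-up apart from periods 1 and 2. A sensible programmer might stop at TP2. The output is also descriptive: the trial was terminated, no hypothesis is tested, and every event is listed by subject. This stands as a limit on the consequences. It does not settle the text, because the only explicit onset rule for double-blind events has no end and two other sections support the open reading.

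A reader might infer more than the documents support:

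- *Observation is lengthened mainly on placebo.* The plan assumes more loss-of-response on placebo, but retreatment depends on biopsy findings, and no arm-specific recurrence rate is given. Both arms stop drug at Week 38. Protocol 3.3.1 reports that 4 of 6 C1-INH-treated pilot subjects needed retreatment, some of them months after stopping. Retreatment is foreseeable in either arm.
- *The percentages have mismatched numerators and denominators.* They do not: the denominator is subjects, and no exposure-adjusted rate is planned. What remains is that the adverse-event and exposure tables may describe different spans.
- *All whole-study tables mix products.* The RWS whole-study summary is restricted to C1-INH subjects. Only the RiS summaries pool.
- *Events move to the wrong arm.* Retreatment repeats the TP2 assignment, so events stay in their arm. The fault is the time window.

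**Conclusion.** The point holds as a defect in the period definition. Taken literally, SAP 11 with 8.3.1, 8.3.2 and 11.2 puts retreatment events, and possibly related follow-up events, into by-arm tables labelled TP2. This is contrary to SAP 8.2.3 in part (depending on its undefined stop date) and to protocol 9.4 and 10.3.4.1, and out of step with SAP 11.1.

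For a subject with one full retreatment, the adverse-event window roughly doubles. In arms of 6 or 7, each such subject with a retreatment-only event shifts the arm's percentage by 14 to 17 points. That size rests on the assumed split and is what any one subject contributes in so small a trial; the documents do not show how many retreatment-only events there are. The direction of any distortion between arms is unknown. No event probability under longer observation is offered, because the documents give no event rate from which to derive one.

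The RiS whole-study tables do pool placebo and C1-INH time. The SAP does not call them incidence on C1-INH, but they carry no warning against that reading. The share of placebo time cannot be worked out, because the size of the RiS set is not given.

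**What to change.** 1. In SAP Section 11, end the TP2 adverse-event window at the earlier of the last TP2 dose plus 30 days and the day before the first retreatment dose. Refer to that window in 11.2, 11.3 and 11.4.
2. Tabulate retreatment adverse events separately by arm, matching the exposure summary in 11.1. Tabulate any later follow-up events separately by arm, with a note that only possibly related events were required to be reported.
3. Reconcile 8.2.3 with 8.3.2 and 11.2 on when treatment emergence ends, and define the investigational product stop date for retreated subjects.
4. Split the RiS whole-study tables by product received at onset, or footnote that they include events during placebo treatment.
5. State that all events of subjects never randomized are open-label; they have no randomization date, so the present rule does not formally classify them.

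The cost is SAP wording and one period and product-at-onset flag in the adverse-event dataset. SAP 8.2.9 already derives the start and end of each retreatment period, so no new data are needed. It should be settled before unblinding.
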